11.6.2.2. Handling of Partial Dates

Element	Reporting Detail
Concomitant Medications	
 • Partial dates for any concomitant medications recorded in the CRF will be imputed using the following convention: 
 • If the partial date is a start date, a '01' will be used for the day and 'Jan' will be used for the month • If the partial date is a stop date, a '28/29/30/31' will be used for the day (dependent on the month and year) and 'Dec' will be used for the month. • The recorded partial date will be displayed in listings.
Adverse Events	
 • Any partial dates for adverse events will be raised to data management. If the full date cannot be ascertained, the following assumptions will be made: 
 • If the partial date is a start date, a '01' will be used for the day and 'Jan' will be used for the month. • However, if these results in a date prior to Week 1 Day 1 and the event could possibly have occurred during treatment from the partial information, then the Week 1 Day 1 date will be assumed to be the start date. • The AE will then be considered to start on-treatment (worst case). • If the partial date is a stop date, a '28/29/30/31' will be used for the day (dependent on the month and year) and 'Dec' will be used for the month. • The recorded partial date will be displayed in listings.

11.6.2.3. Handling of Missing Data for Statistical Analysis/Efficacy Endpoints

Element	Reporting Detail
All Endpoints	
• Missing values will not be imputed.

11.7. Appendix 7: Values of Potential Clinical Importance

11.7.1. Laboratory Values

Haematology				
Laboratory Parameter	Units	Category	Clinical Concern Range	
			Low Flag (< x)	High Flag (>x)
Hematocrit	Ratio of 1	Male		0.54
		Female		0.54
		Δ from BL	↓0.075	
Hemoglobin	g/L	Male		180
		Female		180
		Δ from BL	↓25	
Lymphocytes	GI/L		0.8	
Neutrophil Count	GI/L		1.5	
Platelet Count	GI/L		100	550
White Blood Cell Count (WBC)	GI/L		3	20

Clinical Chemistry				
Laboratory Parameter	Units	Category	Clinical Concern Range	
			Low Flag (< x)	High Flag (>x)
Albumin	G/L		30	
Calcium	mmol/L		2	2.75
Creatinine	umol/L	Δ from BL		↑ 44.2
Glucose	mmol/L		3	9
Magnesium	mmol/L		0.5	1.23
Phosphorus	mmol/L		0.8	1.6
Potassium	mmol/L		3	5.5
Sodium	mmol/L		130	150
Total CO ₂	mmol/L		18	32

Liver Function			
Test Analyte	Units	Category	Clinical Concern Range
ALT/SGPT	IU/L	High	≥ 2x ULN
AST/SGOT	IU/L	High	≥ 2x ULN
AlkPhos	IU/L	High	≥ 2x ULN
T Bilirubin	µmol/L	High	≥ 1.5xULN
T. Bilirubin + ALT	µmol/L U/L	High	1.5xULN T. Bilirubin + ≥ 2x ULN ALT

11.7.2. ECG

ECG Parameter	Units	Clinical Concern Range	
		Lower	Upper
Absolute			
Absolute QTc Interval	msec		> 450
Absolute PR Interval	msec	< 110	> 220
Absolute QRS Interval	msec	< 75	> 110
Change from Baseline			
Increase from Baseline QTc	msec	> 60	

11.7.3. Vital Signs

Vital Sign Parameter (Absolute)	Units	Clinical Concern Range	
		Lower	Upper
Systolic Blood Pressure	mmHg	< 85	> 160
Diastolic Blood Pressure	mmHg	< 45	> 100
Heart Rate	bpm	< 40	> 110
Temperature	°C	35.5	37.5

11.8. Appendix 8 – Abbreviations & Trade Marks

11.8.1. Abbreviations

Abbreviation	Description
AE	Adverse Event
GSK	GlaxoSmithKline
ADA	Anti-Drug Antibodies
AUC	Area under concentration-time curve
AUC($0-\infty$)	Area under the concentration-time curve from time zero (pre-dose) extrapolated to infinite time
BMI	Body mass index
BPM	Beat Per Minute
CL	Systemic clearance of parent drug
Cmax	Maximum observed concentration
CI	Confidence Interval
CV	Coefficient of variance
HR	Heart rate
ICH	International Conference on Harmonization of Technical Requirements for Registration of Pharmaceuticals for Human Use
IDSL	Integrated Data Standards Library
Kg	Kilogram
λ_z	Terminal phase rate constant
LLQ	Lower limit of quantification
NQ	Non-quantifiable concentration measured as below LLQ
PK	Pharmacokinetic
QC	Quality control
RAP	Reporting and Analysis Plan
SAS	Statistical Analysis Software
SI	System Independent
SD	Standard deviation
SOP	Standard Operating Procedure
t OR tlast	Time of last observed quantifiable concentration
$t_{1/2}$	Terminal phase half-life
tlag	Lag time before observation of drug concentrations in sampled matrix
tmax	Time of occurrence of Cmax
ULQ	Upper limit of quantification
ULN	Upper limit of normal
UK	United Kingdom

11.8.2. Trademarks

Trademarks of the GlaxoSmithKline Group of Companies	Trademarks not owned by the GlaxoSmithKline Group of Companies
NONE	NONMEM
	SAS
	WinNonlin

11.9. Appendix 9: List of Data Displays

11.9.1. Deliverable

Delivery	Description
IA1	Interim analysis after recruitment of approximately 8 to 10 patients to review for a consideration of dose adjustment
IA2	Interim analysis once the last patient completes 7-Days post-transplant.
SAC	Final Statistical Analysis Complete

11.9.2. Data Display Numbering

The following numbering will be applied for RAP generated displays:

Section	Tables	Figures
Study Population	1.01 to 1.10	N/A
Efficacy	2.01 to 2.29	2.01 to 2.17
Safety	3.01 to 3.24	N/A
Pharmacokinetic	4.01 to 4.03	4.01 to 4.03
PK/PD	NA	5.01
Section	Listings	
ICH Listings		1 to 19
Other Listings		20 to 41

11.9.3. Study Population Tables

Study Population Tables					
No.	Population	IDSL / TST ID / Example Shell	Title	Programming Notes	Deliverable
Subject Disposition					
1.01	All Subjects	ES1	Summary of Subject Disposition		IA2, SAC
1.02	All Subjects	ES6	Summary of Reasons for Screening Failure		IA2, SAC
1.03	All Subjects	DV1a	Summary of Important Protocol Deviations		IA2, SAC
1.04	All Subjects	SA2	Summary of Deviations Leading to Exclusion from Per Protocol Population		IA2, SAC
1.05	All Subjects	ES5	Summary of Reasons for Withdrawals		IA2, SAC
Demographics					
1.06	All Subjects	DM1	Summary of Demographic Characteristics		IA2, SAC
1.07	All Subjects	DM5	Summary of Race and Racial Combinations		IA2, SAC
1.08	All Subjects	SA1	Summary of Study Populations		IA2, SAC

Study Population Tables					
No.	Population	IDSL / TST ID / Example Shell	Title	Programming Notes	Deliverable
Medical Condition & Con Meds					
1.09	All Subjects	MH1	Summary of [Current/Past] Medical Conditions		IA2, SAC
1.10	All Subjects	CM1	Summary of Most Frequently used Concomitant Medications by Generic Term	Footnote: Most Frequently means the overall concomitant medication used is $\geq 10\%$	IA1, IA2, SAC

11.9.4. Efficacy Tables

Efficacy Tables					
No.	Population	IDS / TST ID / Example Shell	Title	Programming Notes	Deliverable
DGF					
2.01	Analysis Population	Non-Standard EFF_T3	Proportion of Subjects with DGF		IA1, IA2, SAC
2.02	Per Protocol	Non-Standard EFF_T3	Proportion of Subjects with DGF		IA2, SAC
Graft function					
2.03	Analysis Population	Non-Standard EFF_T1	Summary Statistics of Serum Creatinine		IA1, IA2, SAC
2.04	Analysis Population	Non-Standard EFF_T2	Summary of Serum Creatinine Change from Baseline		IA1, IA2, SAC
2.05	Analysis Population	Non-Standard EFF_T1	Summary Statistics of AUC of 7 Day Serum Creatinine	Only consider patients who have Day 7 serum creatinine value	IA1, IA2, SAC
2.06	Analysis Population	Non-Standard EFF_T1	Summary Statistics of AUC of 30 Day Serum Creatinine		IA1, IA2, SAC
2.07	Analysis Population	Non-Standard EFF_T1	Summary Statistics of $\frac{1}{2}$ -Life of 30 Day Serum Creatinine		IA1, IA2, SAC

Efficacy Tables					
No.	Population	IDSL / TST ID / Example Shell	Title	Programming Notes	Deliverable
2.08	All Subjects	Non-Standard EFF_T4	Proportion of Subjects with Renal Functional Graft within 7 Days after Transplant	Including primary non function;3 day functional DGF; 7 day functional DGF; 3 day intermediate graft function; 7 day intermediate graft function; 3 day immediate graft function; 7 day immediate graft function	IA1, IA2, SAC
Acute rejection risk					
2.09	All Subjects	Non-Standard EFF_T3	Proportion of Subjects with Episodes of Biopsy-Proven Acute Rejection		IA2, SAC
2.10	All Subjects	Non-Standard EFF_T2	Summary Statistics of Episodes of Biopsy-Proven Acute Rejection		IA2, SAC
PD biomarker					
2.11	All Subjects	Non-Standard EFF_T1	Summary Statistics of Serum IP-10		IA2, SAC
2.12	All Subjects	Non-Standard EFF_T2	Summary Statistics of Serum IP-10 Change from Baseline		IA2, SAC
2.13	All Subjects	Non-Standard EFF_T1	Summary Statistics of Mig		IA2, SAC
2.14	All Subjects	Non-Standard EFF_T2	Summary Statistics of Mig Change from Baseline		IA2, SAC

Efficacy Tables					
No.	Population	IDSL / TST ID / Example Shell	Title	Programming Notes	Deliverable
2.15	All Subjects	Non-Standard EFF_T1	Summary Statistics of Free IL-18		IA2, SAC
2.16	All Subjects	Non-Standard EFF_T2	Summary Statistics of Free IL-18 Change from Baseline		IA2, SAC
2.17	All Subjects	Non-Standard EFF_T1	Summary Statistics of Bound IL-18		IA2, SAC
2.18	All Subjects	Non-Standard EFF_T2	Summary Statistics of Bound IL-18 Change from Baseline		IA2, SAC
2.19	All Subjects	Non-Standard EFF_T1	Summary Statistics of Total IL-18		IA2, SAC
2.20	All Subjects	Non-Standard EFF_T2	Summary Statistics of total IL-18 Change from Baseline		IA2, SAC
Urine biomarker					
2.21	All Subjects	Non-Standard EFF_T1	Summary Statistics of IL-18		IA2, SAC
2.22	All Subjects	Non-Standard EFF_T1	Summary Statistics of NGAL		IA2, SAC
2.23	All Subjects	Non-Standard EFF_T1	Summary Statistics of KIM1		IA2, SAC

Efficacy Tables					
No.	Population	IDSL / TST ID / Example Shell	Title	Programming Notes	Deliverable
Dialysis dependency and graft survival					
2.24	All Subjects	Non-Standard EFF_T3	Proportion of Subjects Who are Dialysis-Independent at Visits up to 12 Months post Transplant		IA2, SAC
Exploratory					
2.25	All Subjects	Non-Standard EFF_T2	Summary Statistics of % Free GSK1070806 within Renal Graft Biopsies		IA2, SAC
2.26	All Subjects	Non-Standard EFF_T2	Summary Statistics of % Bound GSK1070806 within Renal Graft Biopsies		IA2, SAC
2.27	All Subjects	Non-Standard EFF_T2	Summary Statistics of Level of IL-18 in Renal Preservation Fluid		IA2, SAC
2.28	All Subjects	Non-Standard EFF_T2	Summary Statistics of Serum Cytokine Levels		IA2, SAC
2.29	All Subjects	Non-Standard EFF_T1	Summary Statistics of Length of Hospital Stay		IA2, SAC

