Secondary Analyses	
 Summaries of baseline and post-dose values or proportions of subjects at various time points will be provided. Graft survival will be summarized by Kaplan-Meier plots.

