2.2. Study Objective(s) and Endpoint(s)

Objectives	Endpoints
Primary	Primary

 To assess the frequency of delayed graft function (DGF) in donation after circulatory death (DCD) renal transplant recipients treated with GSK1070806. 	
 Proportion of subjects requiring dialysis during the first 7 days post transplant, (excluding requirement for dialysis due to hyperkalemia within first 24 post-operative hours).
Secondary	Secondary

 To assess graft function in DCD renal transplant recipients treated with GSK1070806. 	
 Serum creatinine at baseline and over time post transplant. Urine output at baseline and over time post transplant. Proportion of subjects in the first 7 days with: 
 Primary Non Function Functional DGF Intermediate Graft Function Immediate Graft Function

 To assess the effect of GSK1070806 on acute rejection risk, and rejection/PD biomarkers. 	
 Proportion of subjects with episodes of biopsy-proven acute rejection. Rejection biomarkers/ PD markers (including serum IP-10 and Mig) at baseline and over time post transplant.

 To assess the effect of GSK1070806 on dialysis dependency and graft survival. 	
 Number of dialysis events per patient in the first 30 days post transplant. Proportion of subjects who are dialysis-independent at visits up to 12 months post transplant.

 To assess the safety and tolerability of GSK1070806 in renal transplant recipients. 	
 AEs and SAEs 
 Clinical laboratory values Vital signs Frequency, type and severity of infections

 To assess the pharmacokinetics of GSK1070806 in renal transplant recipients. 	
 Serum concentrations of GSK1070806 over time, and derived pharmacokinetic parameters if feasible (AUC, Cmax).

Objectives	Endpoints

 To assess the effect of GSK1070806 administration on serum IL-18 levels. 	
 Free, total, and GSK1070806 bound IL-18 at baseline and over time post transplant.

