3.1.2 Planned Interim Analysis

The following interim analyses are planned (protocol defined):

Interim Analysis	Details
During Study	
• The DGF data will be reviewed sequentially.• An interim analysis will be performed after recruitment of approximately 8 to 10 patients to review for a consideration of dose adjustment based on an integrated review of safety/tolerability, efficacy, and exposure.• The preliminary PK data which involves but not limited to GSK1070806 concentrations, total, free, drug bound IL-18 levels as data permit and applicable.• Once the last patient completes 7-Days post-transplant, an interim analysis will be performed of all available data for the primary endpoint in addition to supportive efficacy and safety data. The results of this interim analysis will be reviewed by the GSK study team and other relevant GSK staff for internal decision making.

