4. ANALYSIS POPULATIONS

Population	Definition / Criteria	Analyses Evaluated
All Subjects	
 • Comprise of subjects who receive the dose of study medication. 	
 • Safety/tolerability
Analysis	
 • For DGF related endpoints the 'Analysis Population' (AP) is defined as subjects in the 'All Subjects' population who have been declared to have DGF or have reached 7 days. For other endpoints, the AP is defined as subjects having baseline and at least one post-baseline assessment. 	
 • Efficacy • PD/Biomarker
Per Protocol	
 • Comprised of Analysis Population subjects who are compliant with protocol-specific criteria. Subjects with specified protocol deviations will be excluded per Appendix 1. 	
 • Primary efficacy endpoint
PK	
 • Subjects in the 'All Subjects' population for whom a serum pharmacokinetic sample is obtained and analyzed for GSK1070806. 	
 • PK

NOTE :

- Please refer to Appendix 10: List of Data Displays which details the population to be used for each display being generated.

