Treatment	N	Visit	Planned Relevant Time	n	Mean	S.D	Median	Min	Max
GSK1070806 3 mg/kg	xx	xx	x		XXX.X	XX.XX	XXX.X	XXX	XXX
	xx		x		XXX.X	XX.XX	XXX.X	XXX	XXX
	xx	xx	x		XXX.X	XX.XX	XXX.X	XXX	XXX
	xx		x		XXX.X	XX.XX	XXX.X	XXX	XXX

Example : EFF_T3
Protocol : 204824
Population : All Subjects.

Page 1 of n

Table X
Proportion of Subjects with DGF

	Number of Subjects (%) (N)
Subjects with DGF	XXX (%)

Example : EFF_T4
Protocol : 204824
Population : All Subjects.

Page 1 of n

Table X
Proportion of Subjects with Renal Functional Graft within 7 Days after Transplant

	Number of Subjects (%) (N)
Primary Non DGF	XXX (%)
3 day Functional DGF	XXX (%)
7 day Functional DGF	XXX (%)
3 day Intermediate Graft Function	XXX (%)
7 day Intermediate Graft Function	XXX (%)
3 day Immediate Graft Function	XXX (%)
7 day Immediate Graft Function	XXX (%)

Example : EFF_T5
 Protocol : 204824
 Population : All Subjects

Page 1 of X

Table X
 Summary of Maximum Emergent QTc Values by Category

Baseline (N = xx)				Enhanced Monitoring (N = xx)			
Criteria	N	Mean QTc	SD	Criteria	N	Mean max QTc	SD
QT <= 480 msec	xx	xx.x	xx.xx	QTc > 530 msec	xx	xx.x	xx.xx
				QT (uncorr) > 600 msec	xx	xx.x	xx.xx
Bundle Branch Block with QT <= 500 msec	xx	xx.x	xx.xx	QTc >= 550 msec	xx	xx.x	xx.xx
				QT (uncorr) > 600 msec	xx	xx.x	xx.xx

Note: QTc value could be QTcB or QTcF depends on collected data.

Example : SAFE_L1
 Protocol : 204824
 Population : All Subjects

Page 1 of X

Listing X
Listing of XXX

Treatment	Subj.	Analyte (units)	Visit	Actual Date	Planned Relative Time	Time Sample Taken	Result	Change from Baseline
GSK1070806 3mg/kg	PPD	XXX	DAY 1	PPD	PRE DOSE	9:48	0.9	
			DAY 1		4 Hr	9:48	1.10	0.20
			DAY 29		4 Hr	9:48	2.60	1.70
			DAY 85		4 Hr	9:48	1.10	0.20

NOTE: Table adjusted accordingly to the study data.

Example : SAFE_L2
Protocol : 204824
Population : All Subjects

Page 1 of X

Listing X
Listing of Patients Hospitalization and Re-hospitalization Stay

Subject	Age/Gender	Race	DGF (Y/N)	Hosp. Date	Discharge Date	Length of Stay (Day)
XXXXXXX	XX/X	XX	X	XX/XX/XXXX	XX/XX/XXXX	XX
				XX/XX/XXXX	XX/XX/XXXX	XX
XXXXXXX	XX/X	XX	X	XX/XX/XXXX	XX/XX/XXXX	XX

Example : SAFE_L3
Protocol : 204824
Population : All Subjects

Page 1 of X

Table X
Listing of Donor Virology

Subject	Age/Gender	Race	Virology Type	Positive (yes/no)
XXXXXXX	XX/X	XX	Hepatitis B	
			Hepatitis C	
			HIV	
			EBV	

CONFIDENTIAL

204824

Example : SAFE_L4
Protocol : 204824
Population : All Subjects

Page 1 of X

Table X

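### Table 2.09 reports biopsy-proven acute rejection at IA2 as a crude proportion of all dosed subjects with no time window, so the figure depends on recruitment speed

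*SAP*

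**What the plan says.** SAP Section 2.2 lists the endpoint as "Proportion of subjects with episodes of biopsy-proven acute rejection" under the secondary objective on acute rejection risk, and names no period. Other endpoints in that section do carry a time: 7 days for DGF, 30 days for the number of dialysis events, and visits up to 12 months for dialysis independence.

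Section 11.9.4 assigns Table 2.09, "Proportion of Subjects with Episodes of Biopsy-Proven Acute Rejection", to the All Subjects population and shell EFF_T3, for delivery at IA2 and SAC. The programming notes are blank. Section 4 defines All Subjects as follows: "Comprise of subjects who receive the dose of study medication". No minimum follow-up is required. In Appendix 10, shell EFF_T3 holds one count and percentage over one N, with no column for visit, time or censoring.

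Section 11.9.1 defines IA2 as "Interim analysis once the last patient completes 7-Days post-transplant". Section 3.1.2 adds "Once the last patient completes 7-Days post-transplant, an interim analysis will be performed of all available data" and says that sponsor staff will review the results for internal decisions.

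Graft survival is handled differently. The synopsis states "Graft survival will be summarized by Kaplan-Meier plots", and Figure 2.04 gives that curve to 12 months at both IA2 and SAC.

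**The concern.** At IA2 each subject has been followed from transplant to the data cut, and the shortest planned follow-up is 7 days. Table 2.09 counts a subject seen for one week without rejection exactly like a subject seen for a year without rejection. The percentage then describes rejections seen so far in a cohort with mixed follow-up. It is not the risk over any stated time.

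This matters because the trial has a single arm. A rejection percentage can only be read against an outside rate, and such a rate belongs to a time point. The IA2 figure belongs to none, and against a long horizon it errs towards making rejection look rarer. Graft survival has the same staggered follow-up at the same look and is given a method that allows for it.

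**Working it through.** **The plan's own figures.** The SAP states no rejection rate, so there is no rejection figure to reproduce. Its only design figures are the probabilities of a go decision in the synopsis, 0.139 at a DGF rate of 50% and 0.69 at 35%. A sequential beta-binomial calculation with a Beta(5,8) prior fitted to Figure 1, success at 11 or fewer DGF events in 30, and stops at predictive probabilities above 92% or below 2%, gives 0.1389 and 0.6895. Those figures are sound, concern DGF only, and play no part below.

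**Direction.** Let F(t) be the probability of a first rejection by time t, and let t_i be the follow-up of subject i at IA2, counted up to 12 months. The expected crude proportion is

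(1/N) × Σ F(t_i).

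F never decreases and each t_i is at most 12 months, so this average cannot exceed F(12 months). It is strictly lower if any rejection risk falls after some subject's cut-off. No assumed rate is needed. The statement covers horizons at least as long as the follow-up. Against a short horizon such as 30 days the crude figure can lie on either side.

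**Size: assumptions, none from the SAP.**
- True 12-month risk R = 20%.
- Uniform accrual over A = 6, 12 or 18 months, with the cut 7 days (0.23 months) after the last entry.
- Two timings: constant hazard, or 60% of the 12-month incidence by month 3 with constant hazard within each part.

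The expected crude figure is the mean of F(t) for t uniform on (0.23, 0.23 + A) months, with t capped at 12.

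Constant hazard: λ = −ln(0.80)/12 = 0.0186 per month. For A = 6:

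1 − (e^(−0.23λ) − e^(−6.23λ)) / (6λ) = 1 − (0.9957 − 0.8906)/0.1116 ≈ 0.058.

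Front-loaded: F(3) = 0.6 × 0.20 = 0.12, so the hazard is −ln(0.88)/3 = 0.0426 per month up to month 3. After that it is [ln(0.88) − ln(0.80)]/9 = 0.0106 per month.

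| Accrual | Constant hazard | 60% by month 3 |
|---|---|---|
| 6 months | 5.8% | 10.3% |
| 12 months | 10.8% | 14.0% |
| 18 months | 13.8% | 16.0% |

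With R = 10% and 12 months of accrual the results are 5.3% and 7.0%.

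A wider grid used 30 evenly spaced entries, accrual of 6 to 24 months, R from 10% to 30%, and F(t) = 1 − (1 − R)^((t/365)^k) with t in days and k = 1, 0.5 or 0.3. The crude figure was 28% to 90% of the 12-month risk, and below it in every case.

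**In subjects.** With the maximum of 30, a 20% risk corresponds to 6 expected events. The crude figures of 5.8% to 16.0% correspond to 30 × 0.058 = 1.7 up to 30 × 0.160 = 4.8.

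**What a time-to-event estimate could use at IA2.** Number of 30 evenly spaced entrants (30.4-day months) who have reached each time, before any loss:

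| Accrual | D30 | D90 | 6 months | 12 months |
|---|---|---|---|---|
| 6 months | 26 | 16 | 2 | 0 |
| 12 months | 28 | 23 | 16 | 1 |
| 18 months | 28 | 25 | 20 | 11 |

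Early time points are well supported under all three accrual times. The 12-month point is empty or nearly so under the two shorter ones.

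**The case against.** The SAP names no rejection horizon. A count at a data cut correctly describes what has been observed, and it is low only against a horizon that the reader brings. A window may also stand in the protocol, which is not at hand. The first part is right and limits the wording: the figure is low relative to a common longer horizon, not wrong in itself. The second does not remove the point, because the SAP itself fixes the population, shell and delivery, and a 12-month window would still leave incomplete follow-up at IA2.

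Reviewers at IA2 also have Listing 27, which shows individual rejection episodes; its shell SAFE_L1 has visit and date columns. That stands as partial mitigation, but the listing gives no denominator adjusted for follow-up. Table 2.10 has visit columns too, but its shell EFF_T2 is a change-from-baseline summary and supplies no window. EFF_T3 is a generic example that must be adapted for Table 2.24 as well. There, however, the title asks for results by visit, whereas nothing in Table 2.09 does.

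Precision is poor in any case. For 4 of 30 the exact 95% interval is about 4% to 31%, so the difference at stake is a few events.

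A reader might infer three stronger claims, which the document does not support:
- **That the IA2 decision is biased.** The go/no-go/continue rule in Section 3.1.1 uses DGF only. At IA2 other efficacy data are supportive, and no rejection threshold is stated.
- **That the final analysis has the same fault for every early withdrawal.** Planned follow-up is complete at SAC. Note 13 to the Time and Events table keeps assessments going after withdrawal where possible and asks for the 6- and 12-month safety follow-up. Only subjects truly lost remain.
- **That the size of the shortfall is known.** It rests wholly on assumed accrual, risk and timing.

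**Conclusion.** The point holds for IA2. As written, Table 2.09 gives a percentage without a time base, whose value depends on how fast the trial recruited. In expectation it lies below the 12-month risk if any rejections fall after subjects' cut-off times. The direction follows from the SAP's own definitions.

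The size cannot be derived from the SAP. Under a 20% 12-month risk and 6 to 18 months of uniform accrual, the expected crude figure is about 6% to 16%; it comes closer to the 12-month risk when accrual is slow and rejection comes early. DGF conclusions are untouched, and the matter at SAC is minor. This is an inexpensive improvement to a secondary display, not a threat to the trial's main result.

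**What to change.** **At IA2.** Keep the crude count in Table 2.09. Add a time-to-event estimate of first biopsy-proven acute rejection with numbers at risk. Cumulative incidence with death and graft loss as competing events is preferable. Kaplan-Meier is acceptable if the SAP states that censoring those events overstates rejection incidence. Report it only at those scheduled times (D30, D90, 6 and 12 months) that enough subjects have reached, and set that minimum number in the SAP before the look.

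**At SAC.** State the window as transplant to 12 months, and give the same estimate beside the count.

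**Cost.** One table changes, with a short censoring and competing-event rule. The episode dates are already planned for Listing 27, and the SAP already plans a Kaplan-Meier display for graft survival. The downside is slightly more analysis work and imprecise later time points at IA2, which the numbers at risk will make visible.
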